10.3.2.3 Multiplicity Adjustment

This is a safety study. All efficacy/PD endpoints are secondary endpoints. No multiplicity adjustment will be implemented for these endpoints and the corresponding *P*-values generated for them will be nominal.

10.4 Safety Analysis

Treatment Cohort Period 1

Evaluating safety of long-term treatment with lumacaftor in combination with ivacaftor in the Treatment Cohort Period 1 is the primary objective of this study. The overall safety profile of study drug will be assessed in terms of the following safety and tolerability endpoints:

- Adverse events
- Clinical laboratory values (hematology, serum chemistry, coagulation studies, and urinalysis)
- Standard digital electrocardiograms (ECGs)
- Vital signs
- Pulse oximetry
- Ophthalmological examinations
- Spirometry

Only descriptive analysis of safety will be performed (i.e., no statistical testing will be performed).

10.4.1 Adverse Events

Observational Cohort

For the Observational Cohort, a listing will be presented for all SAEs.

Treatment Cohort Period 1

For Treatment Cohort Period 1, TEAEs will be summarized following the presentation format in Section 10.1.2.1, Table 10-3.

- 1) Previous Study Period based on Safety Set by treatment groups (L200/I and Placebo);
- 2) Current Study Period based on 110 Safety Set by treatment groups (L200/I-L/I and P-L/I) and Overall;
- 3) Cumulative Study Period based on Safety Set with L200/I-L/I, and Current Study Period based on 110 Safety Set with P-L/I, pooled together. The pooled treatment group is presented as L/I Overall.

In TEAE summaries, number and percentage of subjects, as well as exposure-adjusted number of events, will be provided.

For analysis purposes, AEs will be classified as pretreatment AEs, TEAEs, or post-treatment AEs.

- **Pretreatment AE:** any AE that started in the pre-treatment period. The pre-treatment AE will be the same for Previous Study Period and Cumulative Study Period.
- **TEAE:** any AE that increased in severity or that was newly developed in the treatment-emergent period.
- **Post-treatment AE:** any AE that increased in severity or that was newly developed in the post-treatment period.

For AEs with missing or partial start dates, if there is no clear evidence that the AEs started before or after study treatment, then the AEs will be classified as TEAEs. Details regarding handling rules of missing dates are included in Appendix J.

An overview table of the TEAE profile for Treatment Cohort Period 1 will be provided, including total number of TEAEs, with number and percent of subjects and exposure-adjusted number of events in 100PY for the following categories:

- All TEAEs
- Grade 3/4 TEAEs
- TEAEs by relationship
- TEAEs by maximum severity
- TEAEs leading to treatment interruption
- TEAEs leading to treatment discontinuation

- Serious TEAEs
- Related serious TEAEs
- TEAE leading to death

Adverse events summary tables will be presented for the aforementioned TEAEs. The summary will be presented by Medical Dictionary for Regulatory Activities (MedDRA) system organ class (SOC) and preferred term (PT) using frequency counts, percentages (i.e., number and percentage of subjects with one or more events) and exposure-adjusted number of events (i.e., number of events per 100PY). When summarizing the number and percentages of subjects, subjects with multiple occurrences of the same adverse event or a continuing adverse event will be counted once, and only the maximum severity level will be presented in the severity summaries, and the worst/highest relationship level in the relationship summaries.

Additional summary tables will be presented for TEAEs showing number and percentage of subjects, as well as exposure-adjusted number of events per 100PY:

- Any TEAE by PT
- TEAE with a frequency of $\geq 5\%$ at the PT level in any treatment group by PT

For subjects in Study 110 exposed to LUM 400 mg q12h/IVA 250 mg q12h, an overview of the TEAE profile summarizing TEAEs occurring during the treatment-emergent period will be provided, [REDACTED]

In addition, a listing containing individual subject adverse event data for TEAEs leading to treatment interruption, TEAEs leading to treatment discontinuation, SAEs and all deaths will be provided separately, with a flag indicating the TEAE status for SAEs and deaths.

Analysis of AEs of special interest (AESI) categories:

The following AESIs are defined:

1. Elevated Transaminases

The AESI of elevated transaminases is defined by the AEs whose PTs falls into any of the following:

- Alanine aminotransferase abnormal
- Alanine aminotransferase increased
- Aspartate aminotransferase abnormal
- Aspartate aminotransferase increased
- Transaminases abnormal
- Transaminases increased
- Liver function test abnormal
- Liver function test increased

- Hypertransaminasaemia
- Hepatic enzyme increased
- Hepatic enzyme abnormal

2. Respiratory Symptom AESI

The respiratory symptoms AESI is defined by the AEs whose PTs fall into any of the following:

- Chest Discomfort
- Dyspnoea
- Respiration abnormal

3. Respiratory events AESI

The respiratory event AESI is defined by the AEs whose PTs fall into any of the following:

- Asthma
- Bronchial hyperreactivity
- Bronchospasm
- Chest Discomfort
- Dyspnoea
- Respiration abnormal
- Wheezing

Treatment-emergent AESIs will be summarized

- Showing number and percentage of subjects by PT;
- Showing number and percentage of subjects by maximum severity;
- Summary of duration of events (days) with descriptive summary;
- Summary of time-to-first onset (relative to first dose date);
- Showing number and percentage of subjects with 1) TEAE leading to treatment interruption; 2) TEAE leading to treatment discontinuation; 3) serious TEAEs; 4) related serious TEAEs; and 5) TEAE leading to death.

Treatment Cohort Period 2

For Treatment Cohort Period 2, AEs will be classified as TEAEs or post-treatment AEs.

- **TEAE:** any AE that increased in severity or that was newly developed in the treatment-emergent period of Treatment Cohort Period 2.
- **Post-treatment AE:** any AE that increased in severity or that was newly developed in the post-treatment period of Treatment Cohort Period 2.

For AEs with missing or partial start dates, if there is no clear evidence that the AEs started before or after study treatment, then the AEs will be classified as TEAEs. Details regarding handling rules of missing dates are included in Appendix J.

An overview table of the TEAE profile will be provided, including total number of TEAEs, with number and percent of subjects in Treatment Cohort Period 2 for the following categories:

- All TEAEs
- Grade 3/4 TEAEs
- TEAEs by relationship
- TEAEs by maximum severity
- TEAEs leading to treatment interruption
- TEAEs leading to treatment discontinuation
- Serious TEAEs
- Related serious TEAEs
- TEAE leading to death

TEAE tables summarizing number and percentage of subjects with one or more events by SOC and PT will be provided for the following:

- All TEAEs
- Serious TEAEs

When summarizing the number and percentages of subjects, subjects with multiple occurrences of the same adverse event or a continuing adverse event will be counted once, and only the maximum severity level will be presented in the severity summaries, and the worst/highest relationship level in the relationship summaries.

In addition, a listing containing individual subject adverse event data for all AEs, TEAEs leading to treatment interruption, TEAEs leading to treatment discontinuation, and SAEs will be provided separately, with a flag indicating the TEAE status for AEs and SAEs listings.

10.4.2 Clinical Laboratory

Treatment Cohort Period 1

For the laboratory measurements, the raw values and change from previous study baseline of the continuous hematology and chemistry results will be summarized in System International (SI) units at each scheduled time point in the Cumulative Study Period based on the Safety Set.

The number and percentage of subjects meeting the defined threshold criteria during the treatment-emergent period will be summarized. The threshold criteria are provided in Appendix H. For LFT results (alanine aminotransferase [ALT], aspartate aminotransferase [AST], serum alkaline phosphatase [ALP], and total bilirubin), the following analyses will be conducted:

- The mean values (95% CI) will be plotted against visit for all the visits in the Cumulative Study Period for ALT and AST.

- A listing for subjects with elevated LFT results during the treatment-emergent period of the Cumulative Study Period will be presented. The listing will include all parameters of the LFT assessment at all visits.

The number and percentage of subjects with shift changes from baseline in ALT, AST, ALP and total bilirubin (normal/missing, high, low, according to the reference range), based on the worst on-treatment laboratory evaluation, will be tabulated.

Results of urinalysis and the serum pregnancy test will be listed in individual subject data listings only. A listing containing individual subject hematology, chemistry, and coagulation values will be provided with a column indicating outside reference range or not. This listing will include data from scheduled and unscheduled time points.

Treatment Cohort Period 2

For Treatment Cohort Period 2 LFT results (ALT, AST, ALP, and total bilirubin), the following analyses will be conducted:

- The number and percentage of subjects meeting the defined threshold criteria during the treatment-emergent period of Treatment Cohort Period 2 will be summarized. The threshold criteria are provided in Appendix H.
- A listing for subjects with all LFT results during the treatment-emergent period of the Treatment Cohort Period 2 will be presented. The listing will include all parameters of the LFT assessment at all visits.

Results of urine pregnancy test will be listed in individual subject data listing.

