11.7.3 Elevation of Liver Function Test Parameters

It is strongly recommended that subjects with new ALT or AST elevations of $\geq 3 \times \text{ULN}$ and clinical symptoms be followed closely, including repeat confirmatory testing performed by the central laboratory within 48 to 72 hours of the initial finding and subsequent close monitoring of ALT and AST levels, as clinically indicated.

Study Drug Interruption

Study drug administration **must be interrupted** immediately, and the Vertex medical monitor or designee must be notified, if any of the following criteria is met:

- ALT or AST $\geq 8 \times \text{ULN}$
- ALT or AST $\geq 5 \times \text{ULN}$ for more than 2 weeks
- ALT or AST $\geq 3 \times \text{ULN}$ in association with total bilirubin $\geq 2 \times \text{ULN}$ and/or clinical jaundice

A thorough investigation of potential causes should be conducted and the subject should be followed closely for clinical progression.

If no convincing alternative etiology (e.g., acetaminophen use, viral hepatitis, or alcohol ingestion) for the elevated transaminases is identified, regardless of whether ALT or AST levels have improved, study drug treatment must be discontinued, in consultation with the Vertex medical monitor or authorized designee. Subjects in whom treatment is discontinued for elevated transaminases should have their transaminases monitored closely until levels normalize or return to baseline.

Resumption of Study Drug

If a convincing alternative etiology is identified for the elevated transaminases (ALT, AST, and total bilirubin), study drug may be resumed when transaminases return to baseline or are $\leq 2 \times \text{ULN}$, whichever is higher. Approval of the Vertex medical monitor or designee is required before resumption of study drug. Upon resumption of study drug, transaminases should be assessed weekly for 4 weeks. If a protocol-defined transaminase elevation occurs within 4 weeks of rechallenge with the study drug, then the study drug must be discontinued, regardless of the presumed etiology.

Mandatory Liver Function Testing

Liver function testing (ALT, AST, gamma glutamyl transpeptidase, alkaline phosphatase, and total bilirubin) must be performed while subjects are receiving study drug treatment (Day 1, Day 15, and at a minimum of every 4 weeks after Week 4 as noted in [Table 3-1](#)). These blood samples should be processed and shipped immediately per the Laboratory Manual.

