12.4.4.2 Clinical Laboratory Assessments

A summary of raw values and change from baseline values at each visit will be provided for the continuous laboratory results in SI units for current dosing period based on Study 110 Safety Set, and for the active dosing period based on the Integrated Safety Set. For each of the LFTs, mean values will be plotted against visit by treatment arm.

The number and percentage of subjects with shift changes from baseline (normal/missing, high, low, according to the reference range), based on the worst on-treatment laboratory evaluation, will be tabulated.

For subjects with at least 1 potentially clinically significant (PCS) event during the treatment-emergent period, summaries will be presented for each elevation category using number and percentage of subjects as well as number of elevations per 100 patient-year

(number of elevations adjusted for the total duration of exposure). The PCS criteria will be provided in the SAP.

A listing of subjects with elevated LFT results during the treatment-emergent period will be presented including all parameters of the liver function and assessment at all visits.

Results of pregnancy tests will be listed in individual subject data listings only. In addition, a listing containing individual subject laboratory values outside the reference ranges will be provided. This listing will include data from scheduled and unscheduled time points.

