6 STUDY ENDPOINTS

6.1 Primary Endpoint

Treatment Cohort Period 1

Safety and tolerability assessments of long-term treatment of lumacaftor in combination with ivacaftor based on adverse events (AEs), clinical laboratory values (serum chemistry, hematology, coagulation studies, and urinalysis), standard 12-lead electrocardiograms (ECGs), vital signs, pulse oximetry, ophthalmological examinations, and spirometry.

Treatment Cohort Period 2 and Observational Cohort

Not applicable

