Appendix H Criteria for Threshold Analysis

Table 13-9 Threshold Analysis Criteria for Laboratory Tests

Parameter	Threshold Analysis	Comments
Clinical Chemistry		
ALT	$\leq 3xULN$ $>3x - \leq 5xULN$ $>5x - \leq 8xULN$ $>3xULN$ $>5xULN$ $>8xULN$	FDA DILI Guidance Jul 2009.
AST	$\leq 3xULN$ $>3x - \leq 5xULN$ $>5x - \leq 8xULN$ $>3xULN$ $>5xULN$ $>8xULN$	FDA DILI Guidance Jul 2009.
ALT or AST	ALT>3xULN or AST>3xULN	Vertex LFT working group 2014
Alkaline Phosphatase	>1.5xULN	FDA DILI Guidance Jul 2009.
Total Bilirubin	$>1.5x - \leq 2xULN$ $>2xULN$	FDA DILI Guidance Jul 2009.
ALT and Total Bilirubin	ALT>3xULN and TBILI>2xULN	FDA DILI Guidance Jul 2009. To be counted within a same treatment phase, whatever the interval between measurement.
AST and Total Bilirubin	AST>3xULN and TBILI>2xULN	FDA DILI Guidance Jul 2009. To be counted within a same treatment phase, whatever the interval between measurement.
(ALT or AST) and Total Bilirubin	(ALT>3xULN or AST>3xULN) and TBILI>2xULN	Vertex LFT working group 2014
CPK	$>3x - \leq 10xULN$ $>10xULN$	FDA Feb 2005. Am J Cardiol April 2006.
Creatinine	$\geq 150 \mu\text{mol/L}$ (Adults) $\geq 30\%$ change from baseline $\geq 100\%$ change from baseline	Benichou C., 1994.
Creatinine Clearance (Cockcroft's formula)	<30 ml/min (severe renal impairment) $\geq 30 - <50$ ml/min (moderate renal impairment) $\geq 50 - \leq 80$ ml/min (mild renal impairment)	FDA criteria May 1998.
Uric Acid		Harrison- Principles of internal Medicine 17 th Ed., 2008.
Hypouricemia	<120 $\mu\text{mol/L}$	
Hyperuricemia	>408 $\mu\text{mol/L}$	
Blood Urea Nitrogen	≥ 17 mmol/L	
Chloride	<85 mmol/L >115 mmol/L	
Sodium	≤ 129 mmol/L ≥ 150 mmol/L	

Table 13-9 Threshold Analysis Criteria for Laboratory Tests

Parameter	Threshold Analysis	Comments
Potassium	<3 mmol/L ≥5.5 mmol/L	FDA Feb 2005.
Total Cholesterol	≥7.74 mmol/L	Threshold for therapeutic intervention.
Triglycerides	≥4.6 mmol/L	Threshold for therapeutic intervention.
Glucose		
Hypoglycaemia	≤3.9 mmol/L and <LLN	ADA May 2005.
Hyperglycaemia	≥11.1 mmol/L (unfasted); ≥7 mmol/L (fasted)	ADA Jan 2008.
HbA1c	>8%	
Albumin	≤25 g/L	
CRP	>2xULN or >10 mg/L (if ULN not provided)	FDA Sept 2005.
Hematology		
WBC	<3.0 Giga/L (Non-Black); <2.0 Giga/L (Black) ≥16.0 Giga/L	Increase in WBC: not relevant. To be interpreted only if no differential count available.
Lymphocytes	>4.0 Giga/L	

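### SAP 10.4.2 tabulates less laboratory data than the protocol and the primary endpoint call for: coagulation is only listed, and GGT has no shift table or threshold count

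*SAP*

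**What the plan says.** Protocol 7.1 and SAP 6.1 define the laboratory part of the primary endpoint identically: "clinical laboratory values (serum chemistry, hematology, coagulation studies, and urinalysis".

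Protocol 12.4.4.2 plans raw values and changes by visit for the "continuous laboratory results in SI units for current dosing period" (and again for the active dosing period). It also plans counts of subjects with "shift changes from baseline (normal/missing, high, low, according to the reference range), based on the worst on-treatment laboratory evaluation, will be tabulated". Neither sentence names or excludes an analyte. The same section plans a mean plot for every liver test and leaves the criteria for potentially clinically significant values to the SAP.

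On liver tests, Protocol 11.7.3 states: "Liver function testing (ALT, AST, gamma glutamyl transpeptidase, alkaline phosphatase, and total bilirubin) must be performed". The footnotes to the SAP's own schedule (Table 13-1) name the same five tests, and Table 13-2 schedules all five in Treatment Cohort Period 2.

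SAP 10.4.2 summarises by visit as follows: "the raw values and change from previous study baseline of the continuous hematology and chemistry results will be summarized". Its shift table covers "shift changes from baseline in ALT, AST, ALP and total bilirubin (normal/missing, high, low, according to the reference range". Coagulation values go into a listing with a reference-range flag, and urinalysis is listed only. The SAP's liver-test set is ALT, AST, ALP and total bilirubin in both periods. Appendix H, Table 13-9 has no row for GGT or for any coagulation test.

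**The concern.** Safety is the primary objective, and the descriptive tables are the primary analysis. If the SAP is programmed as written, one named part of the primary endpoint (coagulation) yields no table. One of the five liver tests that the protocol makes mandatory yields by-visit means but no count of children with a raised value. Means can hide a small number of marked elevations, which is what shift tables and threshold counts are there to show.

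The gap is wider in Period 2. SAP 6.2 makes liver tests a secondary endpoint there, GGT is drawn, and no by-visit chemistry summary is planned.

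The supplied SAP text gives no reason for the reduction. Section 4 mentions only additional analyses beyond the protocol. Section 3 is not in the supplied text, so an explanation there cannot be excluded.

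**Working it through.** No sample-size or power figure bears on this point. The check compares the sets of tests named in each place.

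**Inputs.** Collected tests: Protocol Table 11-1. Planned outputs: Protocol 12.4.4.2. SAP outputs: SAP 10.4.2 and Appendix H, Table 13-9. Mandatory liver tests: Protocol 11.7.3.

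**1. Laboratory groups in the primary endpoint.**

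| Group | By-visit summary in SAP 10.4.2 | Shift table | Threshold rows in Table 13-9 |
|---|---|---|---|
| Chemistry | yes | four liver tests only | some tests |
| Hematology | yes | none | some tests |
| Coagulation (aPTT, PT, INR) | no | none | 0 of 3 |
| Urinalysis | no (listing) | none | none |

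Two of the four groups are listing-only. Coagulation is the clearer departure: its three tests are continuous, so they fall directly under the protocol's by-visit plan.

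**2. Liver tests.** Protocol: {ALT, AST, GGT, ALP, total bilirubin} = 5. SAP: {ALT, AST, ALP, total bilirubin} = 4. Difference: {GGT}.

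- Period 1: GGT, as a chemistry test, gets the by-visit summary and listings. It has no shift table, threshold count or plot.
- Period 2: the threshold summary names the same four tests. GGT can appear only in the liver-test listing. The supplied protocol version does not cover Period 2, so this comparison is within the SAP: section 6.2 and Table 13-2 against 10.4.2.

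**3. Shift tables.** Counting each numeric item in Table 11-1 once gives 22 chemistry + 13 hematology + 3 coagulation = 38. The SAP tabulates shifts for 4, so 38 − 4 = 34 have none. The protocol sentence reads "The number and percentage of subjects with shift changes from baseline (normal/missing, high, low, according to the reference range" and goes on without limiting the tests.

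**4. Thresholds.** Leaving out the combined ALT/AST/bilirubin rows, Table 13-9 covers 18 chemistry tests. Five are not named in Table 11-1 (uric acid, "Total Cholesterol", triglycerides, HbA1c, CRP), and one, creatinine clearance, is derived. That leaves 18 − 5 − 1 = 12 collected chemistry tests with a threshold and 22 − 12 = 10 without, GGT among them. In hematology, hematocrit has a row but is not named in Table 11-1, so the number of rows outside the panel is at least five.

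**The case against.** **Adverse events capture what matters.** Protocol 11.7.2 and 13.1.1.2 require clinically significant laboratory abnormalities to be recorded as adverse events, and SAP 10.4.1 tabulates these by preferred term with percentages and rates per 100 patient-years. This stands. A reader might infer that GGT or coagulation abnormalities would have no incidence anywhere, and the documents do not support that. But the adverse-event route depends on the investigator's judgement of significance, and the SAP's transaminase list of special interest has no GGT-specific term. It does not replace a count of out-of-range values.

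**The protocol leaves criteria to the SAP.** This also stands. The missing GGT threshold does not breach the protocol, and nine other collected chemistry tests have none either. Nor does Protocol 9.2 make a GGT of at least 3 × ULN a stand-alone abnormality: it is one of four criteria, of which two or more are needed. The by-visit summaries and shift tables are different, because the protocol itself specified them.

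**The general rule in SAP 10.1.2.2 covers all continuous safety variables, and Appendix D gives coagulation visit windows.** This makes the omission less certain but does not settle it. Section 10.4.2 is the specific laboratory text, names two groups, and sends coagulation to a listing. Urinalysis also has windows and is explicitly listing-only.

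**Rows for tests that are not collected.** A reader might infer that five tests are never drawn and that their rows will be empty. That is not shown. The Safety Set includes Study 109 and 011B data, whose laboratory panels are not supplied, and Protocol 11.7.2 allows additional tests.

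**Conclusion.** The point holds as a mismatch between SAP 10.4.2 on one side and Protocol 12.4.4.2 and the primary endpoint on the other. As written, all three coagulation tests have no by-visit summary, shift table or threshold count. One of five mandatory liver tests has no shift or threshold count in Period 1 and at most a listing in Period 2. There would be no tabulated incidence of out-of-range values for either, although those judged clinically significant would be counted as adverse events.

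The analysis is descriptive, so no test or interval is affected. The loss is in the completeness of the primary safety report. The conclusion assumes that 10.4.2 takes precedence over the general rule in 10.1.2.2, and that no unsupplied SAP text restores these tables. It is worth correcting because it concerns the primary endpoint and costs little. The surplus rows in Table 13-9 are housekeeping and change no result.

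**What to change.** In SAP 10.4.2:

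- Add aPTT, PT and INR to the by-visit summaries and the shift table, as Protocol 12.4.4.2 plans.
- Add GGT to the liver-test set and the shift table. Add it to the threshold summary for both periods, with an analysis cut-point in multiples of ULN chosen by the sponsor and entered in Table 13-9.
- For the remaining shift tables that the protocol plans and the SAP omits, and for urinalysis, either restore the output or record the reduction as a change from the protocol with a reason.

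As housekeeping, remove or justify the Table 13-9 rows for tests not named in the Study 110 panel (uric acid, total cholesterol, triglycerides, HbA1c, CRP; check hematocrit).

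The cost is a SAP edit before the final data lock and a few more rows in existing descriptive tables. No new samples or visits are needed.
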